# 8.2.1 Efficacy Endpoints

# 8.2.1.1 Primary Endpoint

[figure not shown]
To assess the safety and tolerability of AGI-134 injected intratumourally, as well as determine the MTD and the recommended Part 2 dose (RP2D).

# 8.2.1.2 Secondary Endpoints

- To characterise the PK profile of AGI-134
- To assess the immune response to AGI-134 and to support the MoA
- To assess biomarkers that may serve as surrogates or predictors of clinical efficacy

# 8.2.1.3 Exploratory Endpoints

Exploratory endpoints will include the following efficacy endpoints:

Protocol AGI-134.FIM.101 CONFIDENTIAL Page 73 of 108

20		PRIVILEGED & CONFIDENTIAL
Investigational Product: AGI-134	A Phase I/IIa, multicentre, two-parts, open label study designed to evaluate the safety and tolerability of escalating	Protocol No. AGI-134.FIM.101
Phase: I/IIa		Version 6.1 31 May 2021

# 8.2.2 Analysis of Safety and Tolerability

Safety parameters (vital signs and laboratory results) will be summarised in listings and presented in tables as changes from Baseline.

ECG examinations results will be displayed in descriptive tables provide the frequency of subjects with abnormal findings for each schedule visit.

AEs will be coded using the latest version of MedDRA (currently version 24.0) and presented in tables by system organ class (SOC), HLT and preferred term. The worst severity grade of AEs, as determined by the latest version of the NCI-CTCAE (currently version 5.0), and their relationship to investigational product will be analysed by SOC, High Level Terms and Preferred Term.

The action taken, and outcome will also be analysed.

By-subject list of AEs, severity grade and relationship will be presented in time-sequence manner using the latest version of NCI-CTCAE (currently 5.0) with SOC, High Level terms and Preferred Term. The number and incidence of subjects experiencing toxicity will be tabulated by worst severity grade in each MedDRA term. The proportion of subjects experiencing toxicity  $\geq$  Grade 3 for each type of toxicity will be calculated.

# 8.3 Ongoing Safety Assessment and Dose-Limiting Toxicity

AEs will be reported from the time of informed consent signature and up to 30 days after the last dose of study drug or until the initiation of new anti-cancer treatment, whichever is sooner. SAEs will be recorded up to 90 days following the last dose of study drug or until the subject initiates new anti-cancer therapy, whichever is earlier.

The period considered for dose-limiting toxicity (DLT) and safety assessment for the accelerated escalation is defined as the time from the first dose administration of AGI-134 and up to the end of the first cycle of therapy (i.e. Cycle 1 - Day 1 through Cycle 1 - Day 21). Data will be reviewed by the Safety Committee. The Safety Committee will be composed of the Study PI together with the Sponsor's MM and Pharmacovigilance Manager (PhV) or designee which will be responsible for the review of all the safety data at pre-defined time points during Part 1 and 2. Safety will be monitored throughout the study.

Beyond the DLT assessment period, data will be assessed continually on an ongoing basis. AEs reported beyond the DLT assessment period will be captured within the eCRF, however will not be considered for DLT assessment period. During Part 2 of the study, any specific AE that fits the DLT definition, occurring at a frequency of >30% will stop accrual. In this situation, the Safety Committee may recommend a lower dose level or dosing schedule change for the continuation of AGI-134 at the RP2D.

Sites will be required to contact the Sponsor within 24 hrs if subjects present with an AGI-134 related AE that is moderate or higher grade and clinically significant or experience DLTs during the DLT assessment period (see Section 3.1.1).

A subject that dropped out of the study will be included in all relevant data analyses and presentation as described in the statistical section.

20		PRIVILEGED & CONFIDENTIAL
Investigational Product: AGI-134	A Phase I/IIa, multicentre, two-parts, open label study designed to evaluate the safety and tolerability of escalating	Protocol No. AGI-134.FIM.101
Phase: I/IIa		Version 6.1 31 May 2021

### 8.3.1 Part 1 – Accelerated Dose Escalation of AGI-134

At any given dose, if one subject presents with a dose-limiting toxicity (DLT) or an event of moderate or higher severity assessed as related to AGI-134 and as clinically significant during the first cycle of treatment, the group of subjects will be expanded and the study will continue in a conventional "3+3" design. The expansion after an event of moderate severity will be to a total of 3 subjects and the expansion after a DLT will be to a total of 6 subjects, recruited in a stepwise manner of 3+3. Moderate injection site reactions are expected events with any injectable drug, as are moderate drug administration-related fever, nausea and vomiting. These will therefore will not be considered as a trigger for conversion to a "3+3" design. If the group of subjects was expanded due to a clinically significant related event that is not a DLT, and this expanded group, i.e. 3 subjects, showed no DLT events, then the study will continue to the next dose level enrolling 3 subjects.

If 1 out of 3 subjects presented with a DLT in the expanded cohort, a group of additional 3 subjects will be treated at the same dose level. If no more DLTs are reported at that dose, i.e. only 1 out of a total of 6 subjects has developed a DLT, the dose escalation will continue to the next level. At any given dose, if 2 or more out of 6 subjects experience a DLT, that dose level will be considered as the DLT dose. In such a case, 3 more subjects will be administered at the previous dose level, if there are less than 6 subjects already treated at that dose. MTD is defined as the highest dose level in which 6 subjects have been administered with and less than 2 instances of DLT.

When the first subject in each dose completes the first cycle of treatment, (each Cycle is 3 weeks long), the safety and tolerability will be assessed by a Safety Committee to decide whether to escalate the dose or to expand the group of subjects. When the MTD is reached or the 200 mg dose is found to be safe, whichever comes first, it will be defined as the RP2D and the study will continue to Part 2.

After completion of the first treatment cycle, subjects in Part 1 of the study will continue receiving intratumoural injection at the dose determined at Screening for 3 additional cycles. No intra-subject escalation will be allowed. The treatment regimen is one dose per cycle of AGI-134 every three weeks for up to 4 cycles.

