	During the first cycle of treatment for each dose, a subject that experiences a dose-limiting toxicity (DLT) or an adverse event (AE) of moderate or high severity, assessed as related to AGI-134 and as clinically significant, will trigger an expansion of the dose level group to a total of three subjects, and the study will continue in a conventional "3+3" design. If the AE is a DLT, an expansion of the dose level to a total of 6 subjects prior to escalation to the next dose level will be triggered and will be performed in a stepwise manner, dosing an additional two subjects in the first dose expansion step, followed by an additional three subjects that would be dosed only if no second DLT occurs.

20		PRIVILEGED & CONFIDENTIAL
Investigational Product: AGI-134		Protocol No. AGI-134.FIM.101
Phase: I/IIa		Version 6.1 31 May 2021

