are reported at that dose, i.e. only 1 out of a total of 6 subjects has developed a DLT, the dose escalation will continue to the next level. At any given dose, if 2 or more out of 6 subjects experience a DLT, that dose level will be considered as the DLT dose. In such a case, 3 more subjects will be administered at the previous dose level, if there are less than 6 subjects already treated at that dose. MTD is defined as the highest dose level in which 6 subjects have been administered with and less than 2 instances of DLT.

When the first subject in each dose completes the first cycle of treatment, (each cycle is 3 weeks long), the safety and tolerability will be assessed by a Safety Committee to decide whether to escalate the dose or to expand the group of subjects. When the MTD is reached or the 200 mg dose is found to be safe, whichever comes first, it will be defined as the RP2D and the study will continue to Part 2.

After completion of the first treatment cycle, subjects in Part 1 of the study will continue receiving intratumoural injection at the dose determined at Screening for 3 additional cycles. No intra-subject escalation will be allowed. The treatment regimen is one dose per cycle of AGI-134 every three weeks for up to 4 cycles.

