#### Part 1:

- a) At each dose level after the first subject has completed the first treatment cycle.
- b) After 3 subjects have completed the first treatment cycle if the dose level was expanded.
- c) After 6 subjects have completed the first treatment cycle if the dose level was expanded due to a DLT.
- d) Following the first assessment of 3 subjects (or 6 if the dose level was expanded) at each cohort, the SC will meet every 6 months on a regular basis to review ongoing safety data and until the LPLV.

Sites will be required to contact the Sponsor within 24 hours if a subject present with a moderate or severe AE related to AGI-134, that is assessed as clinically significant by the Investigator, during the DLT assessment period (see Section 3.1.1). Mild and moderate injection-site reactions will not be considered as a trigger for conversion to a "3+3" design. Other moderate adverse events that are determined to be not clinically significant by the PI will also not be considered as a trigger for conversion to a "3+3" design (see Section 8.3).

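### The Synopsis makes the last three subjects after a DLT conditional on no second DLT; Sections 3 and 8.3.1 omit that condition, and no section classifies 2 or 3 DLTs among three subjects

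*Combined protocol and SAP*

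**What the plan says.** Part 1 doses one subject per level and converts to a 3+3 scheme after a DLT or another qualifying event in the first cycle.

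- **Synopsis, Study Design.** After a DLT the level expands towards six in two steps. A pair of subjects comes first. The second step carries a condition: "followed by an additional three subjects that would be dosed only if no second DLT occurs".
- **Sections 3 and 8.3.1.** After a DLT, "the expansion after a DLT will be to a total of 6 subjects, recruited in a stepwise manner of 3+3". Neither section adds a condition on a second DLT. Both call the scheme a conventional 3+3, and the only branch given for a DLT among three subjects is: "If 1 out of 3 subjects presented with a DLT in the expanded cohort, a group of additional 3 subjects will be treated".
- **DLT dose, in the Synopsis and Sections 3 and 8.3.1 alike.** "At any given dose, if 2 or more out of 6 subjects experience a DLT, that dose level will be considered as the DLT dose". That event triggers treating three more subjects at the previous level if fewer than six were treated there. The MTD is the highest level at which six subjects were treated with fewer than two DLTs.
- **Safety Committee reviews, Synopsis and Section 3.1.** One is scheduled as follows: "After 3 subjects have completed the first treatment cycle if the dose level was expanded". Another follows six subjects if the expansion was due to a DLT. Neither carries a numerical decision rule.
- **Section 9.7.** An expanded dose is assessed after three subjects are recruited, or after more if more than one DLT is reported.

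**The concern.** This is the toxicity rule of a first-in-human escalation, and it is written in two ways. A reader of the Synopsis has an explicit condition on dosing subjects four to six. A reader of Section 3 or 8.3.1 has an expansion to six, a branch for exactly one DLT in three, and a DLT-dose definition that needs six subjects. Faced with two DLTs among the first three, that reader has no sentence to apply. Section 9.7 adds to the uncertainty because it links more than one DLT with assessment after more than three subjects. I found no statement of which section prevails.

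At stake is whether three more subjects are exposed at a level that already has two DLTs, and on what stated basis the level is called the DLT dose and the step back to the previous level begins.

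**Working it through.** **1. The plan's own figure.** Section 8.1 gives a Part 1 maximum of 24. Four levels × 6 subjects = 24, so it reproduces. It is a ceiling and is the same whichever rule applies.

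**2. Which outcomes the visible text covers.**

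| Situation at a level | Synopsis | Sections 3 and 8.3.1 |
|---|---|---|
| Expanded for a DLT; second DLT among the first three | Last three not dosed | No explicit rule; expansion stated as being to six |
| Three subjects, not expanded for a DLT; 1 DLT | Three more treated | Three more treated |
| Three subjects, not expanded for a DLT; 2 or 3 DLTs | No rule | No rule |
| DLT dose declared at 2 or 3 DLTs among three | Not stated | Not stated |
| DLT dose declared at 2 or more of six | Yes | Yes |

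The first row is the contradiction. The third and fourth rows are gaps common to all three places.

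**3. Size.** The documents give no true DLT rate p, so p = 0.1, 0.2, 0.33 and 0.5 are assumptions, with subjects taken as independent and sharing the same p. The path is: subject 1 has a DLT, then two more are dosed.

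- Second DLT in the next two, given a first-subject DLT: 1 − (1 − p)². At p = 0.33: 1 − 0.67² = 1 − 0.449 = 0.551.
- Unconditional chance of that path at a level: p × [1 − (1 − p)²]. At p = 0.33: 0.33 × 0.551 = 0.182.
- Further DLTs expected if three more are treated: 3p. At p = 0.33: 0.99.
- Expected subjects at the level after a first-subject DLT under the Synopsis condition: 3 + 3(1 − p)². At p = 0.33: 3 + 3 × 0.449 = 4.35. The literal body reading gives 6.

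| Assumed p | Second DLT, given first | Unconditional | Further DLTs in three more | Expected subjects, Synopsis | Literal body |
|---|---|---|---|---|---|
| 0.1 | 19% | 2% | 0.3 | 5.43 | 6 |
| 0.2 | 36% | 7% | 0.6 | 4.92 | 6 |
| 0.33 | 55% | 18% | 1.0 | 4.35 | 6 |
| 0.5 | 75% | 38% | 1.5 | 3.75 | 6 |

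**4. Effect on the dose decision.** With two DLTs among three subjects, a count of two or more in six is already certain and the MTD condition of fewer than two in six can no longer be met. Results from three more subjects cannot change that. Escalation after a first-subject DLT requires no DLT in the next five, so its probability is (1 − p)² × (1 − p)³ = (1 − p)⁵ under either reading: 0.59, 0.33, 0.14 and 0.03 at the four rates. Only exposure differs.

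**5. The shared gap.** For any cohort of three, the chance of 2 or 3 DLTs is 3p²(1 − p) + p³ = 3%, 10%, 25% and 50% at the same rates. These figures show how often the unclassified outcome could arise. They do not measure the difference between the Synopsis and the body.

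**The case against.** A reader might infer that Sections 3 and 8.3.1 require three more subjects to be dosed after a second DLT. They do not say so. Both call the scheme a conventional 3+3, recruit stepwise, and attach the second group of three to exactly one DLT in three. The Safety Committee reviews an expanded level after three subjects, and Section 8.3 requires sites to contact the sponsor within 24 hours about DLTs. Going from three to six would therefore not be unreviewed, and a stop can reasonably be read in. Figure 1, the Part 1 diagram, is not shown in the copy reviewed and may contain the missing branch.

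A reader might also infer that the six-subject denominator sets the body against the Synopsis. It does not, because the Synopsis uses the same definition.

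All of this stands, and it limits the point to an omission in the body. It does not remove the conflict. The review after three subjects has no decision rule attached, and Section 9.7 does not supply the stop. Nor can a stop at the second DLT be assumed as the protocol's general practice: for deep lesions in Part 2, one or more DLTs among three subjects leads to three additional subjects, which read literally includes 2 of 3 and 3 of 3.

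Finally, the 55% and 75% figures apply only after a first-subject DLT and at high assumed rates. The unconditional chances, about 2% to 38% over the range shown, are the fairer guide to how often a level would take this path.

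**Conclusion.** Wrong as written: an internal contradiction. For a level expanded because of a DLT, the Synopsis states a condition for dosing subjects four to six that Sections 3 and 8.3.1 omit and Section 9.7 does not restore. Separately, no visible section classifies 2 or 3 DLTs among three subjects. Even if dosing stops as the Synopsis says, the text never formally declares that level the DLT dose or triggers the step back to the previous level.

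The consequence is up to three additional subjects exposed per affected level, with 3p further DLTs expected among them (0.3 to 1.5 over assumed rates of 0.1 to 0.5). A reader might infer that dose selection is also at risk. The documents do not support that, because the escalation probability is the same under both readings and three further subjects cannot rescue the level. The sizes rest on assumed rates, independence between subjects, and the literal reading of the body.

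**What to change.** Reconcile the Synopsis (Study Design, Part 1) with Sections 3, 8.3.1 and 9.7 so that all state the same rule for a second DLT occurring before six subjects have been treated. Say whether that rule also governs three-subject cohorts that were not expanded for a DLT. Make the denominator in the DLT-dose definition agree with it in all three places where the definition appears, so that 2 or 3 DLTs among three subjects is classified and the step back to the previous level has a defined trigger. Check Figure 1 against the result. Which rule to adopt is for the sponsor and investigators; this review proposes none.

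The cost is wording in the Synopsis and Sections 3, 8.3.1 and 9.7. No extra subjects are needed and the maximum of 24 stands.

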#### Study Design

Moderate injection-site reactions, as well as moderate drug administrationrelated fever, nausea and vomiting, are expected events with any injectable drug; hence these will not be considered as a trigger for conversion to a "3+3" design. If the cohort was expanded due to a clinically significant related event that is not a DLT, and the expanded dose level group, i.e., 3 subjects, showed no DLT events, then the study will continue to the next dose level and enrol 3 subjects. If 1 out of 3 subjects experienced a DLT in the expanded cohort, a group of 3 additional subjects will be treated at the same dose level. If no more DLTs are reported at that dose, i.e., only 1 out of a total of 6 subjects has developed a DLT, the dose escalation will continue to the next dose level that will include 3 subjects. At any given dose, if 2 or more out of 6 subjects experience a DLT, that dose level will be considered as the DLT dose. In such a case, 3 more subjects will be treated at the previous dose level, if there are less than 6 subjects already treated at that dose. MTD is defined as the highest dose level in which 6 subjects have been treated with less than 2 instances of DLT.

When each dose level group completes the first cycle of treatment, (each cycle is 3 weeks long), the safety and tolerability will be assessed by a Safety Committee (SC) to decide whether to escalate the dose or to expand the dose level group. When the MTD is reached or the 200 mg dose (the highest dose proposed to be tested) is found to be safe, whichever comes first, it will be defined as the Recommended Part 2 Dose (RP2D) and the study will continue to Part 2.

After completion of the first treatment cycle, subjects in Part 1 of the study will continue receiving intratumoural injections at the dose determined at Screening for 3 additional treatment cycles. No intra-subject escalation will be allowed. The treatment regimen is one dose of AGI-134 per cycle; each cycle is 3 weeks long. The duration of the cycle may be extended if needed to complete additional safety evaluations. Dosing will be given for up to 4 cycles.

98		PRIVILEGED & CONFIDENTIAL
Investigational Product: AGI-134	A Phase I/IIa, multicentre, two-parts, open label study designed to evaluate the safety and tolerability of escalating	Protocol No. AGI-134.FIM.101
Phase: I/IIa	doses of AGI-134 in unresectable/metastatic solid tumours.	Version 6.1 31 May 2021

	 
yê -	T.

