#### Part 1:

- a) At each dose level after the first subject has completed the first treatment cycle
- b) After 3 subjects have completed the first treatment cycle if the dose level was expanded
- c) After 6 subjects have completed the first treatment cycle if the dose level was expanded due to DLT
- d) Following the first assessment of 3 subjects (or 6 if the dose level was expanded) at each cohort.

Safety data will be evaluated by the Safety Committee, who will also meet every 6 months on a regular basis to review ongoing safety data and until the last patient last visit (LPLV).

Sites will be required to contact the Sponsor within 24 hours if a subject present with a moderate or severe AE related to AGI-134, that is assessed as clinically significant by the Investigator, during the DLT assessment period (see Section 3.1.1).

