## 4.5 Removal, Replacement or Early Withdrawal of Subjects from Therapy or Assessment

Subjects are free to discontinue the investigational product and/or their participation in the study at any time and without prejudice to further treatment. The PI must withdraw any subject from the study if that subject requests to be withdrawn, or if it is determined that continuing in the study would result in a significant safety risk to the subject. Subjects that discontinue the investigational product will continue to participate in the Long-Term Follow-up of the study for 5 years, unless they withdraw their consent to continue their participation in the study as well.

Subjects withdrawn from the study prior to the Baseline visit, prior to first injection of AGI-134 or before completion of the DLT assessment period (see Section 3.1.1) will be replaced by the PI to achieve the appropriate number of subjects, regardless of the reason for withdrawal. All data, regardless of DLT period completion or not, will be part of the safety cohort assessment.

If a subject discontinues from the study during the DLT assessment period for any reason other than safety, a replacement subject may be enrolled if deemed appropriate by the PI and Sponsor in order to reach the target number for DLT assessment. Subjects who discontinued the study during the DLT period because of progression will not be considered for DLT assessment; however, they will be counted as having progressed for the efficacy analysis. The replacement subject will be assigned with a unique subject number.

The subject's use of investigational product may be discontinued for any of the following reasons:

- Investigational product toxicity (adverse drug reaction)
- Death
- · Request of regulatory agency
- · Sponsor's request
- PI's request: Investigator decides that withdrawal from the study is in the best interest of the subject
- · Withdrawal of consent by the subject
- Disease Progression
- Female subject who becomes pregnant
- Lost to follow-up

agalin A subsidiary of Bio	nnune DLINERX	PRIVILEGED & CONFIDENTIAL
Investigational Product: AGI-134		Protocol No. AGI-134.FIM.101
Phase: I/IIa		Version 6.1 31 May 2021

- · Subject is non-compliant with study procedures/study protocol
- Other

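### Sections 3 and 8.3.1 time the escalate-or-expand decision at the first subject of each dose, the Synopsis at the dose level group; the two conflict only at levels that open with three subjects after conversion to 3+3

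*Combined protocol and SAP*

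**What the plan says.** Part 1 opens each level (25, 50, 100, 200 mg) with one subject. It converts to 3+3 once a subject has, in cycle 1, a DLT or a clinically significant related event of at least moderate severity, with listed exceptions.

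- **Decision time, body text.** Sections 3 and 8.3.1 use the same words: the Committee assesses safety "When the first subject in each dose completes the first cycle of treatment" in order to choose between escalation and expansion. Nothing limits this to single-subject levels.
- **Decision time, Synopsis (Study Design).** The same choice is made "When each dose level group completes the first cycle of treatment".
- **Size of later levels.** If a level expanded for a non-DLT event shows no DLT in three subjects, "then the study will continue to the next dose level enrolling 3 subjects" (Section 8.3.1). After one DLT in six, the Synopsis says that "the dose escalation will continue to the next dose level that will include 3 subjects".
- **Review schedule (Synopsis and Section 3.1, Part 1).** Item a) is a first-subject review at every level. Item b) reads "After 3 subjects have completed the first treatment cycle if the dose level was expanded". Item c) is a six-subject review after expansion for a DLT. Item d) begins "Following the first assessment of 3 subjects (or 6 if the dose level was expanded) at each cohort"; in Section 3.1 it runs on into the six-monthly meetings.
- **Section 9.7.** Once expanded, a dose is assessed after three subjects are recruited; completion of cycle 1 is not mentioned.
- **DLT window.** Cycle 1 Day 1 to Day 21 (Sections 3.1.1 and 8.3).

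**The concern.** A level that opens with three subjects is one the study runs as 3+3 because a DLT or a clinically significant related event has already occurred at a lower dose. There the first subject is not the group. The body text then places the decision at one completed subject and the Synopsis at three.

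This is a first-in-human trial with 100% dose steps. Followed literally, the body text would allow the next doubling before the second and third subjects have finished their DLT window. The review schedule does not plainly close the gap: on its plain words, item b) applies to a level that was expanded, and a level that opened at three was not.

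**Working it through.** **1. The plan's own figure.** Section 8.1 gives a Part 1 maximum of 24 subjects: 4 levels × 6 = 24. It reproduces and is not in dispute.

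**2. Where the two decision times differ.**

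| Type of level | Sections 3 and 8.3.1 | Synopsis | Conflict? |
|---|---|---|---|
| Opens with 1, no trigger | after subject 1 | after the group, which is subject 1 | No |
| Opens with 1, then expanded | expand after subject 1; later reviews under items b) and c) | same | No |
| Opens with 3 after conversion | after subject 1 | after all 3 | Yes |

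**3. Which decisions are affected.** The 25 mg level always opens with one subject, and no escalation follows 200 mg.

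| Study converts at | Levels opening with 3 | Affected escalation decisions |
|---|---|---|
| 25 mg | 50, 100, 200 mg | 50 to 100 mg; 100 to 200 mg |
| 50 mg | 100, 200 mg | 100 to 200 mg |
| 100 mg | 200 mg | none |
| 200 mg, or never | none | none |

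So at most two decisions are affected, and only if conversion occurs at 25 or 50 mg and a higher level is then opened.

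**4. How much of the window could be unobserved.** If a later subject starts *s* days after the first, then *s* of its 21 days, up to all 21, are still to come when the first subject finishes. The documents set no stagger for these levels, so the range is 0 days (all dosed together) to 21.

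**5. Upper bound on the effect.** The documents give no DLT rate, so *p* = 10% to 50% is assumed. Both formulas count eventual escalation. The expansion path follows the Synopsis, where a DLT leads to "an expansion of the dose level to a total of 6 subjects prior to escalation to the next dose level", and escalation is then allowed with one DLT in six.

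- First subject alone: escalate if subject 1 is DLT-free, or if subject 1 has a DLT and the other five do not: (1 − p) + p(1 − p)^5.
- 3+3: escalate on 0/3, or on 1/3 followed by 0/3: (1 − p)^3 + 3p(1 − p)^5.

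At p = 0.3 the first gives 0.700 + 0.3 × 0.168 = 0.750. The second gives 0.343 + 0.9 × 0.168 = 0.494.

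| Assumed DLT rate | First subject alone | 3+3 | Difference | At least one DLT in subjects 2 and 3, 1 − (1 − p)^2 |
|---|---|---|---|---|
| 10% | 0.959 | 0.906 | 0.053 | 0.19 |
| 20% | 0.866 | 0.709 | 0.157 | 0.36 |
| 30% | 0.750 | 0.494 | 0.256 | 0.51 |
| 40% | 0.631 | 0.309 | 0.322 | 0.64 |
| 50% | 0.516 | 0.172 | 0.344 | 0.75 |

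The first-subject column assumes that no DLT information from subjects 2 and 3 reaches the Committee before it decides. It also disregards the rule in Section 8.3.1 that a DLT in any one subject at a dose expands the group. Non-DLT moderate events are ignored. The differences are therefore an upper bound and not an estimate.

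**The case against.** The strongest reply is that Section 8.3.1, read whole, already requires a group decision. It calls the design after conversion a conventional 3+3 and states its rules per three and per six subjects. At any dose, one subject with a DLT triggers expansion. The disputed sentence says when the Committee meets to choose; it does not say that one DLT-free subject suffices at a three-subject level. Item d) treats three as the size of an unexpanded cohort, which fits a level that opened at three. Section 4.5 provides for replacing subjects "in order to reach the target number for DLT assessment", which presupposes a group target. The Synopsis also lists a first-subject review at each level, so that review can be read as an early check that comes before the group decision. Sites must report DLTs and clinically significant related events of at least moderate grade within 24 hours (Section 8.3), so the Committee would seldom be unaware of a DLT in subjects 2 or 3.

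Most of this stands. It settles the intent and rules out treating the percentages as expected behaviour. A reader might infer that the body text replaces 3+3 with a one-subject rule at these levels. The documents do not support that, because the one-DLT expansion rule and the counts out of three and six sit in the same section.

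It does not remove the conflict in wording. Item d) assumes that a three-subject assessment happens but does not make it a condition for escalating, and in Section 3.1 its function is to set the six-monthly meetings. The 24-hour rule brings in events that have occurred; it cannot supply the part of the window not yet observed. Section 9.7 can be read as covering every dose once the study is in 3+3, but it counts from recruitment. It is a secondary summary and adds little either way.

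**Conclusion.** The point holds as an inconsistency in the text of a first-in-human escalation rule. It is confined to levels that open with three subjects and to at most two escalation decisions. The intended rule is a group decision, and nothing suggests that the sponsor means to escalate on one subject of three. What remains is that the body text, followed to the letter, permits a doubling before the second and third subjects complete their DLT window, and that item b) does not clearly cover such a level.

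A reader might also take the 5 to 34 percentage point differences as the excess chance of escalating under this protocol. They are not. They rest on assumed DLT rates and on a Committee that acts on one subject, against the protocol's own expansion rule. If all three subjects are dosed together, the timing gap almost vanishes. Confidence is high that the wordings differ; the practical risk is small.

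**What to change.** - **Sections 3 and 8.3.1:** time the decision at *when the first subject (single-subject level) or all three subjects (level run as 3+3) complete the first cycle*.
- **Item b) in the Synopsis and Section 3.1:** add *or enrolled three subjects from the start* to the condition.
- **Section 9.7:** count from completion of cycle 1 by three subjects instead of from recruitment.

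The first-subject review in item a) can stay as an early check. The cost is wording in the Synopsis and Sections 3, 3.1, 8.3.1 and 9.7. The Part 1 maximum of 24 and all procedures are unchanged.
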